2.3.1.1 Nonclinical

The toxicity profile of ASP0367 was similar in juvenile and adult rats, with effects targeting the heart; specifically, an increase in the incidence and/or the average grade of myocardial inflammation/necrosis in males, sometimes accompanied by an increased serum cardiac troponin I (cTnI) concentration. Myocardial inflammation/necrosis is a common, age-related background finding in male rats. The greater incidence and/or severity produced by administration of ASP0367 was not observed after dosing was stopped, suggesting the reversibility of these findings.

In juvenile rats, there were no ASP0367-related effects on the development of organ systems that undergo postnatal development, such as the nervous, skeletal and reproductive systems. No microscopic kidney findings similar to those seen in the euthanized cynomolgus monkey (in the 13-week study) were observed in any animals (rats or monkeys) up to 13 weeks of daily dosing, and renal function safety markers were normal in all other animals.

Nonclinical studies have identified the target organs of toxicity as the heart and skeletal muscle. In this phase 2 study in participants with PMM, cardiac (including cTnI, cardiac troponin T [cTnT] and creatine kinase [CK] isoenzymes found in heart muscle [CK-MB]) and skeletal muscle (including total CK and CK isoenzymes found in skeletal and heart muscle [CK-MM]) biomarkers indicative of damage will be measured frequently.

The risk of carcinogenicity has not yet been fully evaluated. Histopathological examination from the carcinogenicity study in rats has been completed and another carcinogenicity study in mice is planned. During the longer-term toxicology studies in adult Wistar Han rats (up to 26-weeks and doses up to 50 mg/kg per day) and in cynomolgus monkeys (up to 52-weeks and doses up to 500 mg/kg per day) no development of tumors was observed. However, in the 26-week rat study a dose-dependent increase in the incidence of hyperplasia of the limiting ridge of the non-glandular stomach and the incidence of hypertrophy/hyperplasia of the follicular cells in the thyroid gland were observed. In the monkey toxicology study, no proliferative lesions were observed during the course of this 52-week study.

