Sequential monitoring for skeletal muscle injury will include assessment of CK, transaminases and lactate dehydrogenase at protocol-specific intervals. An individual participant may be required to discontinue treatment if they develop an elevation in CK levels \geq 5 times the value of the ULN or the individual's baseline value, whichever is higher and it is judged that this elevation is not related to an explainable increase including excessive movement, fall or disease state.

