- Participant who develops any signs or symptoms potentially reflecting cardiac involvement, inclusive of new onset shortness of breath, should interrupt IP and undergo ECG, echocardiogram, and have a cTnI drawn to be evaluated prior to continuing IP.
- Participant who develops an elevation in CK levels ≥ 5 times the value of the ULN or the individual's baseline value, whichever is higher and it has been judged that this elevation is not related to an explainable cause such as excessive activity or disease state.
- Participant who develops elevated levels of ALT or AST > 3 × ULN, or TBL > 2 × ULN persisting after 72 hours in the absence of elevated CK levels must discontinue IP. Generally, liver chemistry will be followed by repeated measurements until they return to baseline or stable values.
- Participant who presents evidence of suicidality during the C-SSRS assessments by meeting the criteria at a level of 4 or 5 since last visit must discontinue IP and upon immediate evaluation, the investigator will decide an appropriate referral.
- Participant who develops symptomatic viral infection should be evaluated by the Investigator and assessed for the need to stop IP until clinically improved.
- Participant who newly develops signs or symptoms of bulbar weakness, such as dysphagia, dysphonia, hoarseness or drooling/sialorrhea, should discontinue IP.
- Participant with a new requirement for oxygen therapy or for ventilatory support, inclusive of any respiratory device to support breathing, such as home ventilators and any form of non-invasive positive pressure ventilation (including CPAP, BiPAP, and AVAPS), should discontinue IP.

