10.4 Appendix 4: Liver Safety Monitoring and Assessment

The purpose of this appendix is to provide guidance for the monitoring of drug-induced liver injury during the course of the study. It should be noted that this section does not specify the end-of-study analyses of liver enzymes. The end-of-study liver enzymes analyses will be described in the SAP. Any participant enrolled in the study with active drug therapy and reveals an increase of serum aminotransferases (AT) to $> 3 \times ULN$ or TBL $> 2 \times ULN$ should undergo detailed testing for liver enzymes (including at least gamma-glutamyltransferase [GGT], ALT, AST, alkaline phosphatase [ALP], TBL and glutamate dehydrogenase). Participants whose baseline ALT or AST values were $> 3 \times ULN$ (with elevated creatine kinase [CK]) and who have a clinically significant rise as assessed by the investigator should also undergo detailed testing for liver enzymes. Testing should be repeated within 72 hours of notification of the test results. For studies for which a central laboratory is used, alerts will be generated by the central laboratory regarding moderate and severe liver abnormality to inform the investigator and study team. Participants should be asked if they have any symptoms suggestive of hepatobiliary dysfunction.

In addition, free triiodothyronine (FT3), free thyroxine (FT4) and thyroid stimulating hormone (TSH) should be measured to monitor the thyroid function in case of hepatobiliary dysfunction. If FT3, FT4 or TSH show any abnormalities and/or clinically significant symptoms, the investigator should determine if further follow up of liver chemistry tests and/or thyroid function tests are required.

For cases with concurrent CK elevation, participants should undergo detailed testing for liver enzymes (including at least GGT, ALT, AST, ALP, TBL and glutamate dehydrogenase). Once the investigator can confirm absence of hepatobiliary injury based on the detailed liver enzyme testing, the investigator will determine if further follow up of liver chemistry tests are required. If concurrent hepatobiliary injury cannot be ruled out, the guidance should be followed as described in Follow-up Procedures in this appendix.

Definition of Liver Abnormalities

Confirmed abnormalities will be characterized as moderate and severe where ULN is as shown below.

Table 9	Moderate and Severe Liver Abnormalities
---------	---

	ALT or AST		TBL
Moderate	$> 3 \times ULN$	or	$> 2 \times ULN$

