10.6 Appendix 6: Clinical Laboratory Assessments

Laboratory tests will be performed according to the schedule of assessments.

Panel/Assessments	Parameters to be Analyzed
Hematology	Hematocrit (Hct)
	Hemoglobin (Hgb)
	Mean corpuscular hemoglobin concentrations (MCHC)
	Mean corpuscular volume
	Platelet count
	Red blood cell count (RBC)
	White blood cell count (WBC)
	White blood cell differential
Biochemistry	Alanine aminotransferase (ALT)
	Albumin (Alb)
	Alkaline phosphatase (ALP)
	Amylase
	Aspartate aminotransferase (AST)
	Blood urea nitrogen (BUN)
	Calcium (Ca)
	Cardiac troponin I (cTnI)
	Cardiac troponin T (cTnT)
	Chloride (Cl)
	C-reacting protein (CRP)
	Creatinine
	Creatine kinase (CK)
	Creatine kinase isoenzymes:
	• Heart muscle (CK-MB) [¶]
	• Skeletal and heart muscle (CK-MM) [¶]
	Cystatin C
	Gamma glutamyl transferase (GGT)
	Glucose (Gluc)
	Glutamate dehydrogenase (GLDH)
	HbA1c
	High-density lipoproteins (HDL)
	Inorganic phosphorus (P)
	Lactate dehydrogenase (LDH)
	Lipase
	Low-density lipoproteins (LDL)
	Magnesium (Mg)
	Plasma lactate
	Potassium (K)
	Sodium (Na)
	Total bilirubin (TBL)
	Total cholesterol (TC)
	Total protein (TP)
	Triglycerides (TG)
	Uric acid (UA)
Table continued on next page	

Table 10Clinical Laboratory Tests

Panel/Assessments	Parameters to be Analyzed
Abbreviated hematology	Hemoglobin (Hgb)
	Platelet count
	Red blood cell count (RBC)
	White blood cell count (WBC)
	White blood cell differential
Abbreviated biochemistry	Alanine transaminase (ALT)
	Alkaline phosphatase (ALP)
	Amylase
	Aspartate transaminase (AST)
	Blood urea nitrogen (BUN)
	Calcium (Ca)
	Cardiac troponin I (cTnI)
	Cardiac troponin T (cTnT)
	Chloride (Cl)
	Creatinine
	Creatine kinase (CK)
	Creatine kinase isoenzymes:
	• Heart muscle (CK-MB) [¶]
	• Skeletal and heart muscle (CK-MM) [¶]
	Cystatin C
	Gamma glutamyl transferase (GGT)
	HbA ₁₀
	Lipase
	Potassium (K)
	Sodium (Na)
	Total bilirubin (TBL)
Serology	Henatitis A virus antibodies
	(immunoglobulin M)
	Hepatitis B surface antigen
	Hepatitis C virus antibodies
	Human immunodeficiency virus 1+2 antibodies
Urinalvsis	Blood
	Creatinine (Cr)
	Glucose
	pH
	Protein
	Urine specific gravity
Pregnancy test (serum)	Human chorionic gonadotropin
Pregnancy test (urine)	Human chorionic gonadotropin
Urine drug test	Amphetamines
-	Barbiturates
	Benzodiazepines
	Cannabinoids
	Cocaine
	MDMA
	Methadone
	Methamphetamines
	Opiates
	Oxycodone
Urine alcohol test	Alcohol

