6.5.2.1 Liver Safety Assessment

The liver safety assessments will be summarized by the categories below based on the measurements from ALP, ALT, total bilirubin, AST and their combination. These parameters will be based on measurements from a local laboratory. If the baseline value is above ULN then use the baseline value instead of ULN.

- ALT > ULN, > 2xULN, > 3xULN, > 5xULN, > 10xULN, > 20xULN
- AST > ULN, > 2xULN, > 3xULN, > 5xULN, > 10xULN, > 20xULN
- ALT or AST > ULN, > 2xULN, > 3xULN, > 5xULN, > 10xULN, > 20xULN
- ALP > 1.5xULN, 2xULN, 2.5xULN
- Total Bilirubin > 2xULN
- (ALT or AST > 3xULN) and Total Bilirubin > 2xULN
- (ALT or AST > 3xULN) and ALP < 2xULN and Total Bilirubin > 2xULN

The last 2 criteria where 2 or more parameters are evaluated will be with the measurements on the same day or up to 1 day apart.

The denominator for each criterion will be the number of participants who have at least one value after the day of first dose taken to 28 days after the last dose of IP for the 52 weeks or moving to the OLE, whichever comes first. The number and percentage of participants meeting the criteria by 28 days after the last dose of IP for the 52 weeks or moving to the OLE will be summarized by analysis group.

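### The liver safety tables in both SAPs count ALT/AST categories without reference to CK, GLDH or GGT, so new muscle-origin rises are counted as liver findings

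*SAP*

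**What the plan says.** Appendix 4 of the protocol gives guidance on monitoring and defers the analysis: "The end-of-study liver enzymes analyses will be described in the SAP". Section 6.5.2.1 of the 52-week SAP and of the 76-week SAP is where that analysis appears. In both, the categories are "based on the measurements from ALP, ALT, total bilirubin, AST and their combination": ALT, AST and ALT-or-AST at six multiples from > ULN to > 20xULN, ALP at three multiples, bilirubin > 2xULN, and two combination rows that require bilirubin > 2xULN together with ALT or AST > 3xULN. One rule applies to all of them: "If the baseline value is above ULN then use the baseline value instead of ULN". CK, GLDH and GGT do not appear.

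Elsewhere in the SAPs these analytes fall only under the by-visit descriptive summaries of biochemistry (Section 6.5.2). CK also enters a separate skeletal muscle AESI (Section 6.5.1). Neither output is joined to ALT/AST within a participant.

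The protocol treats transaminases differently. Section 2.3.1.3 states: "Sequential monitoring for skeletal muscle injury will include assessment of CK, transaminases and lactate dehydrogenase". Exclusion criterion 6 and its footnote read AST/ALT against CK. The liver rule in Section 8.1 concerns elevations "persisting after 72 hours in the absence of elevated CK levels must discontinue IP". Appendix 4 gives concurrent CK elevation its own path, with detailed testing that includes GGT and GLDH, to establish whether hepatobiliary injury is absent.

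**The concern.** In primary mitochondrial myopathy, ALT and AST can come from muscle as well as liver, and the protocol says so by its own rules. Appendix 4 foresees participants with baseline ALT or AST > 3xULN and raised CK. Muscle is also a nonclinical target: "Nonclinical studies have identified the target organs of toxicity as the heart and skeletal muscle". A liver table that ignores CK can mislead in two directions.

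- **Spurious liver findings.** A new muscle-origin rise enters the ALT, AST and ALT-or-AST rows. If the drug affected muscle, these rows could show a dose-related pattern labelled as liver safety.
- **Uncounted liver findings.** In a participant whose baseline is high because of muscle disease, the substituted baseline raises every threshold. A liver injury on top of it may not reach the > 3x row, nor the combination rows that depend on it.

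In arms this small, one or two cases can decide how the table is read.

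**Working it through.** The plan states no figure on this point, so there is none to reproduce. The check is a comparison of text, then two short calculations.

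**Where CK enters**

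| Place | Uses CK with ALT/AST? |
|---|---|
| Protocol 5.2, exclusion 6 and footnote | Yes |
| Protocol 2.3.1.3, muscle monitoring | Yes, transaminases listed with CK and LDH |
| Protocol 8.1, liver rule | Yes |
| Protocol Appendix 4, work-up with raised CK | Yes, with GGT and GLDH |
| Protocol Appendix 4, Table 9, added severe criteria, Hy's Law text | No |
| SAP 6.5.2.1, both SAPs | No |

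**What is collected.** In protocol version 9.0 (Appendix 6, Table 10), ALT, AST, CK and GGT are in both the full and the abbreviated biochemistry panels. GLDH is in the full panel only. The abbreviated panel serves weeks 1, 2, 3, 8, 16 and 20, which are six of the ten post-baseline visits in Table 1 (weeks 1, 2, 3, 4, 8, 12, 16, 20, 24 and 28). The SAPs say that all participants took part under version 7.0 or earlier, and that panel is not in the documents.

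**Effect of baseline substitution.** Let b be baseline divided by ULN. For a row at k times, the threshold in ULN units is k × max(1, b).

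- b = 3, k = 3: 3 × 3 = 9xULN.
- b = 4, k = 3: 3 × 4 = 12xULN.
- b = 4, k = 2: 2 × 4 = 8xULN.

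With b = 4, a rise to 11xULN appears in the > ULN and > 2xULN rows but not in the > 3xULN row. As the rule is written, it then also misses both combination rows, whatever the bilirubin. The substitution deals with a stable elevation present at entry. It does nothing for a muscle-origin rise that starts on treatment in a participant with normal baseline.

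**Illustrative size.** The documents give no rate of muscle-origin ALT/AST > 3xULN, so p is an assumption shown as a range. The expected number per arm is n × p, and P(at least one) = 1 − (1 − p)^n. Two arm sizes are used: the planned 22, and 11, which is the 33 participants of the interim analysis (SAP 6.7.1) divided by 3 with an equal split assumed. The final number per arm is not stated.

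| n per arm | p | Expected | P(at least one) |
|---|---|---|---|
| 11 | 5% | 0.55 | 0.43 |
| 11 | 20% | 2.2 | 0.91 |
| 22 | 5% | 1.1 | 0.68 |
| 22 | 20% | 4.4 | 0.99 |

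**Laboratory source.** Section 6.5.2.1 of both SAPs says the liver parameters come from a local laboratory. SAP 5.4.6, 76-week SAP 5.2.6 and Table 1 footnote g of the protocol say that safety laboratory tests are central. Until this is settled, it is not known whether the ALT/AST in the liver table and the CK come from the same sample.

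**The case against.** The case against is substantial, and much of it stands.

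- **The multiples are not raw.** The baseline rule removes most stable elevations present at entry. This stands, and it narrows the first problem to new rises. The same rule creates the second problem.
- **The SAP does not contradict the protocol.** Table 9, the additional severe criteria and the Hy's Law text in Appendix 4 carry no CK term, and the SAP rows follow that structure. A reader might infer that the protocol reads ALT/AST with CK everywhere; it does not. But Appendix 4 hands the end-of-study analysis to the SAP, so the SAP is where its CK path should be reflected.
- **Other outputs help.** The bilirubin rows are harder for a muscle rise to meet. The 52-week SAP has a randomized placebo arm. CK has an AESI, laboratory data are listed (protocol 9.4.3.2), and Appendix 4 provides a liver abnormality CRF. This stands in part. The bilirubin rows do not check CK. A placebo arm balances disease-related rises but not a drug effect on muscle, and the 76-week SAP has no concurrent placebo group. The AESI needs CK at least 5 times the higher of ULN and baseline plus a matching TEAE, so smaller CK rises do not reach it. Listings permit case review, but the planned summary does not show it.
- **A hard CK split could hide a liver case.** A marked ALT rise with trivially raised CK would fall in the muscle column. This stands, and it means that CK should be added to the table without removing any case from it.

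A reader might also infer that the drug is known to injure human muscle. The documents do not support that. Section 2.3.1.3 calls it an important potential risk seen in rats but not monkeys, and Section 2.3.1.2 reports no drug-related skeletal muscle AEs in the completed phase 1 studies.

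**Conclusion.** The concern holds as a defect in the planned summary. Followed as written, Section 6.5.2.1 of both SAPs counts new muscle-origin rises in the ALT, AST and ALT-or-AST rows. It can also leave a liver injury on a muscle-derived baseline out of the > 3x and combination rows. The mitigating outputs are partial.

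It would go too far to conclude that the trial cannot separate liver from muscle injury, or that no liver conclusion is possible. The protocol provides for the tests to be collected, and individual cases can be worked through from the listings and the liver abnormality CRF.

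The number of affected participants cannot be derived from the documents. The figures of about 0.6-2.2 per arm (11 per arm) and 1.1-4.4 per arm (22 per arm) rest wholly on an assumed 5-20% rate and, for the smaller arms, on an equal split of 33. They make no allowance for baseline substitution. They show only that a handful of such cases could make up much of an arm's count.

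**What to change.** In Section 6.5.2.1 of both SAPs:

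1. Keep the existing rows unchanged.
2. Add a cross-classification of the ALT, AST and ALT-or-AST categories by concurrent CK, for example above ULN or not, using the same-day or up-to-1-day rule that the SAP already applies to combinations. Present it alongside the main counts, and do not use it to remove cases.
3. For each participant with ALT or AST > 3xULN, or meeting a bilirubin combination row, list CK, GGT and, where available, GLDH. Apply the > 3xULN trigger to the actual ULN, so that participants with a substituted baseline are not lost.
4. Reconcile the local laboratory named in 6.5.2.1 with the central laboratory named in SAP 5.4.6, 76-week SAP 5.2.6 and Table 1 footnote g, so that the cross-classified values come from one source.

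If the SAPs can no longer be amended, document the addition in the CSR, as the SAP introduction provides for changes.

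The cost is a few table rows and one listing. The downsides are small cells, GLDH missing where only the abbreviated panel was drawn, and GLDH availability under protocol version 7.0 or earlier, which must be confirmed first. The CK cross-classification does not depend on GLDH.

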- g. Safety laboratory will be done by a central laboratory from the screening to EOS. Blood collection for hematology and biochemistry; muscle biomarkers include CK, CK MM, CK-MB and cardiac troponins I and T. Urinary creatinine should be analyzed quantitatively like blood creatinine analysis that will be used for correcting urinary TITIN. Biochemistry and hematology samples will be taken prior to study assessment, except for ECG and vital signs. At follow-up phone call visits, abbreviated biochemistry (including cardiac troponin I) will be collected at the participant's home (abbreviated hematology will only be collected at week 2) by a qualified healthcare provider from the home healthcare vendor. In case the home healthcare visit is not feasible, the visit can be conducted at the study site.
- h. Serum pregnancy tests will be performed for WOCBP.
- i. Urine pregnancy tests will be performed for WOCBP.
- j. ECGs should be performed prior to blood draw. ECGs will be recorded in triplicate (3 separate ECGs with 5-minute resting prior to first ECG and at least 1 minute apart per time point). In addition, ad hoc triplicate ECG may be required to follow up on an elevation of cTnI above the ULN (see Appendix 10.9 for reference range), or when there is an elevation of cTnT above the ULN (see Appendix 10.9 for reference range) or above the participant's baseline value if it was elevated, or when a participant has any signs or symptoms reflecting cardiac involvement, inclusive of new onset shortness of breath. If the QTcF > 450 msec in male participants and > 480 msec in female participants at screening or randomization, one additional triplicate ECG can be performed on the same day in order to determine the participant's eligibility. ECGs at weeks 2 and 8 will be performed at the participant's home by a qualified healthcare provider from the home healthcare vendor. In case the home healthcare visit is not feasible, the visit can be conducted at the study site.
- k. At screening, the "Screening" version is to be used to determine eligibility. During all subsequent visits, the "Since Last Visit" version is used to monitor on-study suicidal ideation and behavior after the initial assessment.
- 1. Following randomization, participants will be encouraged to perform all 6MWTs within a 2-hour window of the performance time recorded during visit 2.

Footnotes continued on next page

- CONFIDENTIAL -

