7.11 Total Amount of Blood

The total amount of blood for each participant will vary depending on the course of their disease, duration on treatment and local laboratory requirements. At any time during the study, if any laboratory abnormalities are found for a participant, additional blood may be drawn for safety monitoring [Table 7].

Sample Type	Number of Samples	Approximate Sample Volume (mL)	Approximate Total Volume (mL)
Hematology, biochemistry, serology and serum pregnancy test (if applicable) at screening	1	22	22
Biochemistry and hematology at weeks 0, 4, 12, 24 and 28	5	16	80
Abbreviated biochemistry and abbreviated hematology at week 2	1	11.5	11.5
Abbreviated biochemistry at phone call visits	5	10.5	52.5
Pharmacokinetics of ASP0367	4	2	8
Serum biomarkers	3	4	12
Genotyping	1	2	2
Pharmacogenomics (banking)*	1	4	4
Pharmacodynamics of PPAR _δ target gene expression	3	5	15
Total			207

Table 7Blood Volume

PPAR6: peroxisome proliferator-activated receptor delta

*Pharmacogenomics (banking) will be performed for the participants who were given the consent.
8 **PARTICIPANT DISCONTINUATION**

Refer to [Section 10.1.9 Study and Site Start and Closure] regarding discontinuation of study sites or of the study as a whole. An interim analysis will be performed to determine if efficacy or futility stopping criteria are met while the study is ongoing. Refer to [Section 9.6] for details regarding the interim analysis and stopping criteria.

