1 INTRODUCTION

This SAP contains technical and detailed elaboration of the principal features of the analysis described in the protocol and includes procedures for executing the statistical analysis to fulfil the objectives of the study.

The study was designed to be, and executed as, a double-blinded with an OLE. The OLE was removed from protocol version 9.0 and so, the use of the present tense is no longer accurate. In addition to the objectives and endpoints defined in Study 0367-CL-1201 protocol (core protocol), some additional objectives and endpoints specific to the Mayo Clinic (Minnesota) had been defined in Study 0367-CL-1201 [MAYO] Protocol. However, as there have been no participants recruited to the protocol from the Mayo sites, therefore there will be no SAP created. Until protocol version 7.0, the double-blinded period was 52 weeks and open label extension period was 24 weeks. However, from protocol version 8.0 onwards, the doubleblinded period was revised to 24 weeks and in protocol version 9.0 the OLE period was removed. Since no participants have been evaluated under protocol version 8.0 or later, two SAPs will be prepared: one for analyses up to 52 weeks of treatment (the double-blind part of the study), and the other one for analyses at the end of 76 weeks of treatment (the doubleblind part and the OLE part of the study). In analysis for the double-blind part and the OLE part of the study, participants assigned ASP0367 in the double-blinded period will be analyzed for through the double-blinded part and the OLE part of the study including followup visit, while participants switched from Placebo to ASP0367 in the OLE part will be analyzed in the OLE part only including follow-up visit.

This document is an analysis plan for 52 weeks (double-blinded part) including follow-up visit which correspond to protocol v7.0. However, inferential analyses for efficacy endpoints will be conducted at week 24 aligned with protocol v9.0.

Analyses for pharmacokinetic and pharmacodynamic (target gene expression and biochemical markers) endpoints, including exposure-response assessment, will be described in the separate analysis plan and this SAP only focus on efficacy and safety endpoints.

This document will be finalized prior to the database lock at the end of study. If there are any changes from the planned analyses in the final version of the SAP that impact the statistical analyses, then it will be documented in the CSR.

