5.4.6 Laboratory test (hematology, biochemistry and urinalysis)

Safety laboratory tests will be done by a central laboratory from the screening to the end of the study. The scheduled visit and the list of clinical laboratory tests are described in the protocol.

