6.5.2 Clinical Laboratory Evaluation

Quantitative values including hematology, biochemistry, and urinalysis will be summarized using mean, standard deviation, minimum, maximum and median by analysis group at each analysis visit. Additionally, a within-participant change will be calculated as the post-baseline measurement minus the baseline measurement and summarized in the same way. Each laboratory result will be classified as low (L), normal (N), or high (H) at each visit according to the site supplied reference ranges. For the Placebo and ASP0367 groups, baseline values for CK-MM and CK-MB will be defined as the last non-missing observation prior to the first administration of ASP0367.

Frequency tabulations of qualitative clinical laboratory variables (urinalysis) will be presented for each analysis group at each visit.

Additionally, amylase, lipase and troponin elevations above the ULN and 2xULN will be summarized by analysis group. The denominator for each criterion will be the number of participants who have at least one value after the day of first ASP0367 taken to 28 days after the last dose of ASP0367. The number and percentage of participants meeting the criteria by 28 days after the last dose of ASP0367 will be summarized by analysis group.

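### Both SAPs base the liver threshold tables on a local laboratory, although the same SAPs and the protocol have safety chemistry run centrally

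*SAP*

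**What the plan says.** Section 6.5.2.1 of both SAPs sets out summaries of ALT, AST, ALP, total bilirubin and their combinations, by multiples of the ULN. On the source of the values it says: "These parameters will be based on measurements from a local laboratory". The next sentence adds: "If the baseline value is above ULN then use the baseline value instead of ULN". The denominator for each criterion is the participants with one or more values in the counting period. The wording of the source sentence is identical in the two SAPs.

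Section 5.4.6 of the 52-week SAP says: "Safety laboratory tests will be done by a central laboratory from the screening", continuing to the end of the study. Section 5.2.6 of the 76-week SAP has the same sentence. Footnote g to the protocol's schedule of assessments (Table 1) agrees: "Safety laboratory will be done by a central laboratory from the screening to EOS".

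The 76-week SAP alone, in 6.5.2, also classifies laboratory results as low, normal or high "at each visit according to the site supplied reference ranges".

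**The concern.** The liver threshold tables are where the report will show, group by group, how many participants crossed each enzyme or bilirubin limit. Safety and tolerability relative to placebo is a primary objective, so these tables carry weight even though they are descriptive.

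A threshold table needs three things fixed in advance: which measurements enter, whose reference range defines the ULN, and who is in the denominator. All three depend on the laboratory. If the SAP names a laboratory that has no scheduled role in measuring these analytes, none of the three is properly defined. The tables would also draw on different data from the general biochemistry summaries beside them in the same report.

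**Working it through.** No arithmetic tests this point. The check is to set the statements about laboratory source side by side.

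1. **Are the four analytes part of the centrally tested safety laboratory?** Yes. Protocol Table 10 (Appendix 6) lists ALT, AST, ALP and total bilirubin under both the full and the abbreviated biochemistry panels. The central-laboratory statements in both SAPs and in footnote g therefore cover them.

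2. **Is local liver chemistry scheduled anywhere?** No. The home visits at the phone-call weeks change who draws the blood; footnote g still sends the safety laboratory samples to the central laboratory. The protocol's only mention of local laboratory requirements is in 7.11 and concerns total blood volume.

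3. **Could local values exist at all?** Possibly. Section 7.11 says that after a laboratory abnormality "additional blood may be drawn for safety monitoring". Appendix 4 asks for repeat liver testing, and section 10.3.5 provides for further laboratory tests in the follow-up of any adverse event. Sections 7 and 7.2 let routine-care procedures done before consent serve for screening or baseline. None of these passages says which laboratory runs the test.

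4. **What follows from the literal rule?**
   - *Measurements:* scheduled central results do not enter.
   - *Denominator:* a participant with only central results has no qualifying value and drops out of both numerator and denominator.
   - *Reference range:* every limit is a multiple of a ULN, so the range would be that of whichever local laboratory ran the test, or would be missing.
   - *Baseline rule:* it needs a baseline from the same source, and no local baseline is scheduled.
   - *Combined rows:* ALT or AST and bilirubin must be measured no more than a day apart, so both must come from the chosen source.

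5. **How much of the output depends on the sentence?** All of 6.5.2.1: in each SAP 6 ALT limits + 6 AST + 6 for either enzyme + 3 ALP + 1 bilirubin + 2 combined = 24 limits.

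6. **Site-supplied ranges.** This phrase governs the low/normal/high classification only, not the liver multiples. It raises the same question of whose range applies, so it should be settled together with the source.

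**The case against.** The strongest reply is that this is a slip in one sentence and that any programmer would use the central data. That may be so. The table specifications, which might settle it, are not among the documents. Against it, both SAPs distinguish central from local reading for ECGs, and the same sentence stands in two SAPs finalized on the same date. Even if it is a slip, the text should be corrected.

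A second reply is that the protocol supplied is version 9.0, while the SAP introductions say: "Since no participants have been evaluated under protocol version 8.0 or later". The schedule that participants actually followed is not available, so Table 1 cannot be used to count the results that would be left out. This limits the size of the point but not the point itself: each SAP was finalized with that history known and still contradicts itself.

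A third reply concerns protocol Appendix 4, where "alerts will be generated by the central laboratory regarding moderate and severe liver abnormality". That sentence applies to studies that use a central laboratory. It is generic wording and only supporting evidence. The contradiction does not need it.

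Three stronger readings are tempting, and the documents do not support them.

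- A reader might infer that the tables would consist mainly of participants already flagged for liver abnormality. Extra tests are also foreseen for any adverse event, and nothing says who has local values.
- A reader might infer that liver injury could go undetected. Appendix 4 monitoring, serious event reporting, unblinded review by the safety board, the laboratory listings and the general biochemistry summaries do not depend on this sentence.
- A reader might infer that replacing the ULN by a raised baseline is itself an error. The rule is stated openly, and Appendix 4 leaves the end-of-study liver analyses to the SAP. It is a choice of analysis, not a contradiction.

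**Conclusion.** The point holds as a contradiction of data source in both SAPs. As written, 6.5.2.1 names a laboratory for which no liver chemistry is scheduled, and literal use would misdefine the numerators, denominators and reference ranges of every liver threshold row.

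Confidence is high in the textual conflict and lower in its consequences. How many participants have a local result, and how many counts would change, cannot be worked out from the documents; the effect may be nil if the tables were programmed on central data. The conclusion assumes only that the central-laboratory statements describe what was done. Three separate statements, one in each SAP and one in the protocol, point that way. It should be fixed because the error affects the between-group liver tables and is cheap to correct.

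**What to change.** In 6.5.2.1 of both SAPs, replace the source sentence with one stating that the liver tables use central laboratory measurements and central laboratory reference ranges. In 76-week SAP 6.5.2, reconcile the site-supplied ranges with that source. If the SAPs are locked, record the correction and the source actually used in the clinical study report, which is where both SAPs place changes that affect the analyses.

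The cost is one sentence in each SAP and one phrase in the 76-week SAP. If the programming already reads central data, no output changes. If not, the liver tables need one rerun. No extra table and no change to the baseline rule is needed to resolve the contradiction.
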